6.4 Protocol Therapy Discontinuation

In addition to discontinuation from therapy related to toxicities as outlined in section 6.2.1, a subject will also be discontinued from protocol therapy and followed up per protocol under the circumstances

outlined below. The reason for discontinuation of protocol therapy will be documented on the electronic case report form (eCRF).

- Subject has received 6 cycles of study drugs (in the Phase II neoadjuvant cohort)
- Documented radiographic progression (Phase I or Phase II)
- The treating physician/designee thinks a change of therapy would be in the best interest of the subject
- The subject requests to discontinue protocol therapy, whether due to unacceptable toxicity or for other reasons
 - If a subject decides to prematurely discontinue protocol therapy (“refuses treatment”), the subject should be asked if he may still be contacted for further scheduled study assessments. The outcome of that discussion should be documented in both the medical records and in the eCRF.
- If protocol therapy is interrupted for ≥ 28 days from the expected day of the next treatment.

If ipatasertib is permanently discontinued due to toxicity, darolutamide may continue per protocol. If darolutamide is permanently discontinued due to toxicity, ipatasertib should also be discontinued and the patient should proceed to prostatectomy (Phase II).

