7.2 Long Term Follow-up Evaluations

Subjects in the Phase I cohort will not have any long term follow-up evaluations.

All subjects in the Phase II neoadjuvant cohort will be followed every 6 months for two years following prostatectomy or until documented biochemical recurrence. If a subject does not undergo prostatectomy and does not have documented disease progression, he will be followed for disease progression every 6 months for 2 years. Follow up may be accomplished via clinic visit, phone call, or other avenues as appropriate. In cases of disease recurrence the choice of followup therapy will be as per the treating physician. However, adjuvant or salvage therapy should not start until after PSA and testosterone level results are obtained at least four weeks after surgery.

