12.7.2 Phase II (Neoadjuvant Cohort)

In the Phase II neoadjuvant cohort, if after 9 evaluable patients there are no patients with exceptional response (defined as pCR or MRD), accrual will halt due to lack of efficacy. Accrual will not pause while the 9th patient is on therapy, so additional patients may accrue prior to pathologic evaluation of the 9th radical prostatectomy.

For the Phase II neoadjuvant cohort, an additional *early stopping rule for safety* will also be followed throughout the duration of the study. If, at any time, 2 or more patients experience a delay in time to prostatectomy of >28 days after the final dose of ipatasertib (i.e., a delay of > 1 week beyond the allowed timeline of 7-21 days) *due to an ipatasertib-related AE*, the study and all study treatment will be stopped. An ipatasertib-related AE is defined as an AE that is possibly, probably, or definitely related to ipatasertib. Should the study stop early, discussion of reopening the study using modified ipatasertib treatment regimens may be considered after discussion between the PI and Genentech, and after approval by the DSMC.

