13. TRIAL MANAGEMENT

13.1 Data and Safety Monitoring Plan (DSMP)

This study will be conducted in compliance with the Data Safety Monitoring Plan (DSMP) of the Robert H. Lurie Comprehensive Cancer Center of Northwestern University.

BTCRC AHQ oversight activities include:

- Review and processing of all adverse events requiring expedited reporting as defined in the protocol
- Provide trial accrual progress, safety information, and data summary reports to the sponsor-investigator
- Submit data summary reports to the lead institution DSMC and attend DSMC reviews:
 - during the Phase I portion of the study, monthly to present safety summary reports
 - during the Phase II neoadjuvant portion of the study, as applicable: following any reports of protocol deviations that meet IRB expedited reporting requirements, continued non-compliance or SAEs; and overall study data delinquency that exceeds 10% incomplete forms or sites with data delinquency that are not responding sufficiently to the BTCRC AHQ data delinquency escalation process
 - throughout the study, semi-annual comprehensive DSMC review

- During the Phase I portion of the study there will be weekly safety calls with all participating institutions. During the neoadjuvant portion of the study there will be monthly calls with all participating institutions

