13.2 Robert H. Lurie Comprehensive Cancer Center's Data Safety Monitoring Committee

BTCRC AHQ will provide the following for the Robert H. Lurie Comprehensive Cancer Center's DSMC to review:

- Adverse event/ serious adverse event summary report
- Monitoring reports
- Audit results if applicable
- Study accrual patterns
- Data delinquency
- Protocol deviations
- Annual report, prior to submission to the FDA (if the study is under an IND).

The Robert H. Lurie Comprehensive Cancer Center's DSMC will conduct a comprehensive study review semi-annually, based on the date the study was originally opened with NU. Ad hoc reviews may be performed as necessary to ensure patient safety and data integrity. Documentation of DSMC reviews will be provided to sponsor-investigator and BTCRC AHQ. Issues of immediate concern by the DSMC will be brought to the attention of the sponsor-investigator and other regulatory bodies as appropriate. The sponsor-investigator will work with BTCRC AHQ to address the DSMC's concerns.

Link to the Robert H. Lurie Comprehensive Cancer Center's Data and Safety Monitoring Plan:
<https://www.cancer.northwestern.edu/docs/research/data-safety-monitoring-plan.pdf>

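### The only formal Phase II safety stopping rule does not name death before prostatectomy as an event, and it is unclear whether surgery never performed counts

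*Combined protocol and SAP*

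**What the plan says.** Section 12.7.2 sets two stopping rules for the neoadjuvant cohort. One is for futility after 9 evaluable patients. The other is a safety rule that "will also be followed throughout the duration of the study". The safety rule is met, at any time, when "2 or more patients experience a delay in time to prostatectomy of >28 days after the final dose of ipatasertib" and the cause is an ipatasertib-related AE. Attribution is broad: "An ipatasertib-related AE is defined as an AE that is possibly, probably, or definitely related to ipatasertib". When the rule is met, the study and all study treatment stop. Reopening needs discussion with the drug supplier and approval by the DSMC. The threshold is explained as "a delay of > 1 week beyond the allowed timeline of 7-21 days".

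The DLT-based termination rule in 12.7.1 applies to Phase I only.

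Three other places bear on the rule:

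- Section 7.2 foresees men who never have surgery ("If a subject does not undergo prostatectomy and does not have documented disease progression") and gives them follow-up, but does not connect them to 12.7.2.
- Section 6.4 separates the two oral drugs: "If ipatasertib is permanently discontinued due to toxicity, darolutamide may continue per protocol".
- Footnote 3 of the Phase II study calendar places prostatectomy within 28 days (±14 days) of the end of cycle 6.

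On oversight, 13.1 sends Phase II reports to the DSMC "following any reports of protocol deviations that meet IRB expedited reporting requirements, continued non-compliance or SAEs", and also provides a semi-annual review. Section 13.2 adds: "Ad hoc reviews may be performed as necessary to ensure patient safety and data integrity". Neither section gives a count or rate at which the trial must stop.

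**The concern.** The rule guards against toxicity that costs a man with potentially curable disease his timely operation. It measures this only as elapsed time to surgery. A man who dies of ipatasertib toxicity before the 28 days have run has no delay to measure, so he contributes nothing to the count. Two late operations would close the trial automatically; two such deaths would not.

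A man whose operation is called off for toxicity falls in a grey area. One site might count him once day 28 has passed, while another might wait for an operation date that never comes. With a trigger of only 2, one disagreement of this kind can decide whether the rule is met.

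**Working it through.** **1. Which outcomes the wording captures.** Take a man with an ipatasertib-related AE and count days from his last ipatasertib dose.

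| Outcome | Counted under 12.7.2 as written? |
|---|---|
| Operated after day 28 | Yes |
| Alive and unoperated on day 29, surgery later cancelled | Ambiguous: the threshold has passed, but the text does not say he counts |
| Dies unoperated after day 28 | Ambiguous for the same reason |
| Dies unoperated on or before day 28 | No, under any reading |

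**2. Whether the limit is itself settled.** Two differences within the documents need to be reconciled.

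- Section 12.7.2 assumes a window of 7-21 days after the last ipatasertib dose and triggers beyond 28 days. The calendar footnote allows 28 + 14 = 42 days after cycle 6. A man operated on between day 29 and day 42 can be inside the calendar window and still be an event under 12.7.2.
- The clock in 12.7.2 starts at the last ipatasertib dose. If ipatasertib stops for toxicity at the end of cycle 3 and darolutamide continues through cycle 6, then 3 × 28 = 84 days pass before surgery is due. Read literally, a man operated on schedule could be counted.

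**3. Figures in the plan.** The safety rule has no stated operating characteristic to reproduce. The Phase II design figures do reproduce. Exact two-stage power (9 then 17 patients, continue on ≥1 response, success on ≥3) at a 30% response rate is 90.45%, against the stated 90.5%. Enrolment is 17/(1 − 0.15) = 20. So n = 20 is the right full-accrual denominator.

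**4. Chance that the rule is met.** The documents give no rates of toxicity-related delay, death or lost surgery; every rate below is an assumption. With event rate p per man and a trigger of 2,

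P(X ≥ 2) = 1 − (1 − p)^n − n·p·(1 − p)^(n−1).

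For n = 20:

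- p = 0.02: 1 − 0.6676 − 0.2725 = 0.060
- p = 0.05: 1 − 0.3585 − 0.3774 = 0.264
- p = 0.07: 1 − 0.2342 − 0.3526 = 0.413
- p = 0.10: 1 − 0.1216 − 0.2702 = 0.608
- p = 0.15: 1 − 0.0388 − 0.1368 = 0.824

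The delay-only column uses p = delay rate. The all-events column uses p = delay rate + rate of death or no surgery. The last column repeats the comparison with n = 9, as a rough guide to the effect of halting at the futility look.

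| Delay | Death or no surgery | n = 20, delay only | n = 20, all events | n = 9, delay only vs all |
|---|---|---|---|---|
| 0% | 2% | 0% | 6.0% | 0% vs 1.3% |
| 2% | 5% | 6.0% | 41.3% | 1.3% vs 12.7% |
| 5% | 5% | 26.4% | 60.8% | 7.1% vs 22.5% |
| 5% | 10% | 26.4% | 82.4% | 7.1% vs 40.1% |
| 0% | 10% | 0% | 60.8% | 0% vs 22.5% |

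In these scenarios the n = 20 gaps are upper bounds, for two reasons. The delay-only column assumes that no unoperated man is already counted as a delay. Full accrual is also assumed; in every row shown, the gap is smaller with 9 men.

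**The case against.** The strongest reply is that oversight already covers this. Under 11.2.3.1, SAEs at least possibly related to study drug reach the coordinating headquarters within 1 business day. Under 11.2.3.4, the sponsor-investigator is sent a summary within 1 further business day of that receipt. Section 13.1 links Phase II DSMC reports and reviews to SAEs and adds monthly site calls, and 13.2 allows ad hoc review. A reader might infer that two toxic deaths would pass unnoticed or that the trial would simply continue. The documents do not support that: the deaths would be reported, and the DSMC could act. What remains is that action would be discretionary, while two delays stop the study by rule. Cancelled surgery is also less visible than death. It is not an SAE criterion in 11.1.2, and surgery status is not on the 13.2 list of items sent to the DSMC.

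Three further objections stand:

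- A reader might infer that cancelled operations are definitely excluded. They are not. The rule applies at any time and does not require that surgery eventually take place, so a living man unoperated on day 29 can be counted. The fault there is ambiguity.
- A reader might infer that every man who moves to other treatment has fared worse than a man operated on late. Section 1.1 lists radiation with ADT beside prostatectomy as a typical option, so the documents do not show this.
- The 15% attrition in 12.3 is an allowance for non-evaluable patients. It says nothing about toxicity or lost surgery and cannot serve as an event rate.

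Finally, 13.1 places the study under an institutional monitoring plan that is not part of these documents. Statements about what rules exist are therefore limited to the protocol and its statistical section.

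**Conclusion.** The point holds in two parts of different strength. Death before day 29 from an ipatasertib-related AE is outside the only formal Phase II safety stopping rule in these documents; this follows from the wording and needs no assumed rate. Surgery never performed is undefined under the rule, not excluded from it.

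The size depends wholly on assumed rates. At full accrual the gap between counting delays only and counting all three events is 6 points when the only events are death or no surgery at 2%, about 34 to 35 points in the 5%/5% and 2%/5% scenarios, and 61 points when there are no delays and 10% death or no surgery. The real gap may be much smaller. If every affected man were alive and unoperated on day 29 and sites counted him, it would be zero. The clarification is worth making because the outcome the rule certainly misses is death, and the change is small.

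**What to change.** First reconcile the limit. Section 12.7.2 (7-21 days after the last ipatasertib dose, trigger beyond 28 days), the Phase II calendar footnote (28 days ±14 days after cycle 6) and 6.4 (darolutamide continuing after ipatasertib stops) need one agreed window and one agreed start for the clock. Which is right is for the sponsor to decide.

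Then define the monitored event in 12.7.2 as any of the following, each due to an ipatasertib-related AE as that section already defines it:

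- prostatectomy delayed beyond the limit;
- prostatectomy not performed;
- death before prostatectomy.

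Keep the existing trigger of 2. State that an unoperated man counts on the day the limit passes, without waiting for an operation date. Report the probability that the rule is met over a range of event rates, so that the DSMC knows how it behaves.

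The drafting cost is the revised definition plus the reconciliation of the windows. Sample size, doses and the trigger do not change. The statistical cost is a higher chance of stopping, and it is not negligible: under the assumed rates of 5% and 5%, up to 61% instead of 26% in 20 men. The sponsor should accept this knowingly.

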6. TOXICITIES AND DOSE DELAYS/DOSE MODIFICATIONS

The NCI Common Terminology Criteria for Adverse Events (CTCAE) v5 will be used to grade adverse events.

Subjects enrolled in this study will be evaluated clinically and with standard laboratory tests before and at regular intervals during their participation in this study as specified in Study Calendar & Evaluations.

Subjects will be evaluated for adverse events (all grades), serious adverse events, and adverse events requiring study drug interruption or discontinuation as specified in Study Calendar & Evaluations.

Risks associated with ipatasertib

Hyperglycemia, including cases of Grade 3 or Grade 4 hyperglycemia, has been reported in patients receiving ipatasertib as monotherapy or ipatasertib in combination with other anticancer drugs or hormonal therapy. Hyperglycemia of any grade, regardless of causality, was reported in 35.3% of patients who received ipatasertib as a single agent in the Phase I Study PAM4743g, with Grade 3 hyperglycemia occurring in 1 patient (2.0%). In the GO27983 study, hyperglycemia of any grade, regardless of causality, was reported in 22.6%, 9.1%, and 7.4% of patients in the ipatasertib 400 mg, 200 mg, and placebo arms, respectively. Grade 3 hyperglycemia occurred in 10.7%, 2.3%, and 2.5% of patients in the 400 mg, 200 mg, and placebo arms, respectively. One patient (1.2%) in the ipatasertib

400 mg arm experienced Grade 4 hyperglycemia. There were no other instances of Grade 4 or higher hyperglycemia events in any arm. In the GO29227 study, hyperglycemia of any grade, regardless of causality, was reported in 9.5% and 3.3% of patients in the ipatasertib 400 mg and placebo arms, respectively. There were no reports of Grade ≥ 3 hyperglycemia.

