6.3 Ipatasertib Dose Levels for Dose Reductions

Dose level	Dose of Ipatasertib		
Starting Dose	400 mg daily	300 mg daily	200 mg daily
Dose level (-1)	300 mg daily	200 mg daily	Remove from study drugs

Dose level (-2)	200 mg daily	Remove from study drugs	--
Dose level (-3)	Remove from study drugs	--	--

If a dose level below that included in the above table is required the subject will be removed from protocol mandated treatment and will be followed up per protocol and proceed to prostatectomy.

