Glucose value 250 to 500 mg/dL (> 13.9–27.8 mmol/L)	
 Interrupt ipatasertib dosing until fasting hyperglycemia resolves to <160 mg/dL or better. Initiate home glucose monitoring Treat hyperglycemia as medically appropriate. Start (or increase

	
dose of) oral anti-diabetic medications (e.g., metformin).
 
 • Ipatasertib should be reduced by one dose level when treatment is restarted. • If hyperglycemia w/ a glucose value between 250-500 mg/dL recurs, permanently discontinue ipatasertib.
Glucose value > 500 mg/dL (> 27.8 mmol/L); life-threatening consequences	
 • Interrupt ipatasertib dosing until resolution to Grade 1 or better. • Treat hyperglycemia as medically appropriate. • Initiate home glucose monitoring • Start (or increase dose of) oral anti-diabetic medications (e.g., metformin). • Assess for volume depletion and appropriate intravenous or oral hydration. • Permanently discontinue ipatasertib.

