6.3.1.5 Rash

Ipatasertib should be permanently discontinued for rash associated with Stevens-Johnson syndrome, toxic epidermal necrolysis, or other suspected severe hypersensitivity or allergic reaction. Dosage modification and symptom management guidelines for skin toxicity attributable to study treatment are shown in below.

Severity of Rash	Management Guideline
Grade 1	
 Continue study drugs. Consider topical corticosteroids.
Grade 2	
 Interrupt ipatasertib treatment until resolution to Grade 1 or better or the toxicity is no longer clinically significant. Treat rash with topical corticosteroids. Consider treatment of rash with oral corticosteroids.
Grade 3	
 Interrupt ipatasertib treatment until resolution to Grade 1 or better or the toxicity is no longer clinically significant. Treat rash with topical and systemic corticosteroids. Consider dermatological consultation. If the skin toxicity resolves to Grade 1 or better or is no longer clinically significant within 28 days, following completion of the steroid taper, ipatasertib may be resumed at one dose level below the previous dose. If recovery of the skin toxicity to Grade 1 or better does not occur or skin toxicity remains clinically significant continuously for 4 weeks, or Grade 3 rash recurs, permanently discontinue ipatasertib.

Severity of Rash	Management Guideline
Grade 4	
 Administration of systemic steroids (oral or intravenous) is recommended. Consider dermatological consultation and skin biopsy. Ipatasertib should be permanently discontinued.

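### The Phase II safety stop derives its 28-day trigger from a 7-21 day surgical window that the study calendar does not use, so surgery within the calendar can count toward halting the trial

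*Combined protocol and SAP*

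**What the plan says.** Section 12.7.2 sets an early stopping rule for safety that applies throughout Phase II. The study and all treatment stop if "2 or more patients experience a delay in time to prostatectomy of >28 days after the final dose of ipatasertib", provided the cause is an AE at least possibly related to ipatasertib. The rule glosses the 28 days as more than a week "beyond the allowed timeline of 7-21 days". A stop need not be final: "discussion of reopening the study using modified ipatasertib treatment regimens may be considered", subject to agreement with the drug's supplier and approval by the data and safety monitoring committee (DSMC).

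The schedule is set elsewhere:

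- Phase II study calendar, footnote 3: prostatectomy is timed from the end of the sixth cycle, at 28 days with a tolerance of 14 days either way.
- Section 6.1: held or missed doses do not change how long a man is treated before surgery.
- Section 6.4: "If ipatasertib is permanently discontinued due to toxicity, darolutamide may continue per protocol".
- Section 6.3.1: several rows stop ipatasertib alone. If glucose of 250-500 mg/dL "recurs, permanently discontinue ipatasertib" is the instruction; for Grade 4 rash it is "Ipatasertib should be permanently discontinued".
- Section 6.3: a man who needs a dose below the table takes a different route, in which "the subject will be removed from protocol mandated treatment and will be followed up per protocol and proceed to prostatectomy".

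**The concern.** A stopping rule that acts on two men should agree with the schedule that sites follow. This one differs from it in two respects.

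The main one is the window. Section 12.7.2 names 7-21 days as what is permitted and builds its trigger on that. The calendar permits surgery up to 42 days after cycle 6. A site working to footnote 3 has no sign that part of its permitted range lies beyond the stopping threshold.

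The secondary one is the start of the clock. The rule counts from the last ipatasertib dose, whereas surgery is timed from the end of cycle 6. The two dates coincide for a man who takes ipatasertib to the end, but they separate when ipatasertib alone is stopped early for toxicity.

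At stake is an unneeded or disputed halt of a cohort planned at 20 enrolled and 17 evaluable men, with the decision on who counts made after the event.

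**Working it through.** **The plan's own figure.** Upper limit of the window in 12.7.2 plus one week: 21 + 7 = 28 days. The trigger is consistent with its stated premise.

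**The premise against the calendar.** Footnote 3 gives a latest day of 28 + 14 = 42 after cycle 6. The same one-week allowance would then give 42 + 7 = 49 days. The 7-21 day window appears nowhere else in the readable text (the schema figures could not be checked).

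**Fully dosed man.** Six cycles of 28 days end on day 6 × 28 = 168. If his last ipatasertib dose is on day 168, days since the final dose equal days since the end of cycle 6, and the start of the clock makes no difference.

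| Surgery, days after cycle 6 | Calendar footnote 3 | Section 12.7.2, if moved by an ipatasertib-related AE |
|---|---|---|
| 22-28 | permitted | outside the stated window, not counted |
| 29-42 | permitted | counted toward stopping |
| beyond 42 | deviation | counted toward stopping |

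Days 29 to 42 are 14 days. Footnote 3 can be read as days 14-42 (29 days) or days 0-42 (43 days), so this is 14 of 29 or 14 of 43 permitted days. These are shares of the calendar, not probabilities that surgery falls there. On the first reading the two windows share only days 14-21; on the second, 7-21 lies wholly inside footnote 3. The upper limit is 42 on both, so the days 29-42 result does not depend on the reading.

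**Man who stops ipatasertib early and continues darolutamide to day 168.** Interval = 168 + (days from end of cycle 6 to surgery) − (day of last ipatasertib dose).

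- Last dose day 140, surgery 7 days after cycle 6: 168 + 7 − 140 = 35 days.
- Last dose day 112, surgery 7 to 21 days after cycle 6: 175 − 112 = 63 to 189 − 112 = 77 days.
- Last dose day 149 with the hold never lifted, surgery 21 days after cycle 6: 189 − 149 = 40 days.

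All three exceed 28 days. All three operations fall inside the 7-21 days of section 12.7.2 when counted from the end of cycle 6, and none was postponed.

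**Not affected by the clock.** Men who resume ipatasertib after a hold and take it to the end of cycle 6, and men sent to surgery under section 6.3 because they need a dose below the table.

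**The case against.** The best reply on the window is that a safety trigger tied to one drug's AEs may properly be stricter than a general scheduling tolerance. Footnote 3 covers surgery timing for any reason and says nothing about stopping; only 12.7.2 states a trigger, and for a fully dosed man it is explicit. That is right as far as it goes. The two places do not give rival stopping rules, and a reader should not infer that they do. What remains is that 12.7.2 does not present itself as stricter than the schedule. It presents 7-21 days as the schedule, and the calendar says otherwise.

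On the clock, the reply is stronger. The rule requires a *delay* caused by an ipatasertib-related AE, not merely a long interval. A man who stops ipatasertib on day 112 and is operated on time has had no operation delayed, and section 6.1 supports that view. A reader might infer that every early stopper with on-schedule surgery counts; the text does not establish this. It does, however, measure the delay in days from the final ipatasertib dose and makes no exception for these men, so the point stands as an ambiguity.

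The error is also toward caution, reopening is provided for, and the two-stage efficacy design is untouched. These points limit the importance but do not remove the mismatch.

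**Conclusion.** The window mismatch holds and depends on no assumed rate. For fully dosed men, surgery on days 29-42 after cycle 6 that is moved there by an ipatasertib-related AE is within the calendar and counts toward a two-man stop. Late surgery for other reasons does not count.

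The clock point is smaller. For men who stop ipatasertib for good before the end of cycle 6 and continue darolutamide, the rule leaves open whether on-schedule surgery counts.

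A reader might go further and infer a substantial chance of a false stop. The documents do not support a figure. They give no ipatasertib discontinuation rate, section 6.4 says only that darolutamide may continue, and any such figure would rest on the disputed literal reading. The nearest data are event rates, and they differ between studies. In GO27983 one patient (1.2%) in the "400 mg arm experienced Grade 4 hyperglycemia" and one (1.2%) had Grade 4 rash, while GO29227 at the same dose reported no hyperglycemia of Grade 3 or higher and no Grade 4 rash. The case for a change rests on the inconsistency in a decision threshold and on the low cost of removing it.

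**What to change.** **(a) One window.** State the same surgical window in section 12.7.2 and in footnote 3, and set the trigger one week beyond its upper limit. The safety-conservative default is to change footnote 3 to 7-21 days and keep the trigger at more than 28 days. The cost is that surgeries on days 22-42, which the calendar now permits, become deviations. The alternative, keeping an upper limit of 42 days, would move the trigger to more than 49 days and relax the rule by 49 − 28 = 21 days. That should be done only as a deliberate choice by the sponsor.

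**(b) One clock.** Start the count at the end of cycle 6, or on the date both oral study drugs are permanently stopped if that is earlier. Count a man only if surgery is postponed beyond the trigger chosen under (a) because of an ipatasertib-related AE. The same number must appear in both parts of the rule. This settles the position of men who stop ipatasertib early but continue darolutamide.

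Both changes are wording in section 12.7.2 and footnote 3. They need no added patients, visits or data.
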